#### 9.5.1.5.7 OTHER SAFETY ASSESSMENTS

##### **Pregnancy Test**

A serum  $\beta$ -hCG pregnancy test will be performed for all female subjects at Visit 1. On Visit 2 (Day 1) and thereafter, a urine  $\beta$ -hCG pregnancy test will be performed for women of childbearing potential (ie, premenopausal women or postmenopausal women who have been amenorrheic for less than 12 months).

If Visit 1 and Visit 2 are the same day and a result of serum pregnancy test can be assessed by the local laboratory during the day, urine pregnancy test at Visit 2 is not required.

#### 9.5.1.6 Other Assessments

##### **EuroQol 5 Dimensions 5 Levels**

Quality of life will be assessed using the EQ-5D-5L questionnaires at the visits as designated in the Schedule of Procedures/Assessments (Table 3, Table 4, and Table 5).

Questionnaires should be self-read and self-completed unless the subject has a physical disability that prevents him or her from doing so. In these cases, a caregiver or study coordinator should read and/or record the subject's answers.

#### 9.5.2 Schedule of Procedures/Assessments

Table 3, Table 4, and Table 5 present the schedule of procedures/assessments for the study.

Subjects will continue to receive perampanel until 3 or less months from the date of approval of perampanel monotherapy in each country or the sponsor discontinues the study.

**Table 3 Schedule of Procedures/Assessments (Pretreatment Phase to 4 mg Treatment Phase) in Study E2007-J000-342**

| Phase Period   | Pretreatment Phase a | 4 mg Treatment Phase               |        |                    |                                      |         |         |         |         |         | Follow-up Phase b,c |                                |  |
|--|---------------------------------|------------------------------------|--------|--------------------|--------------------------------------|---------|---------|---------|---------|---------|--------------------------------|--------------------------------|--|
|  |                                 | 4 mg Titration Period a |        |                    | 4 mg Maintenance Period b |         |         |         |         |         |                                |                                |  |
| Study Week(s) (from Day 1 of Titration Period)               | Week –4                         | –                                  | Week 2 | Week 4             | Week 6                               | Week 10 | Week 14 | Week 20 | Week 26 | Week 32 | 4 weeks after the last dose    |                                |  |
| Study Day(s) (from Day 1 of Titration Period)                | Day –28 to 1                    | Day 1 m                 | Day 15 | Day 29             | Day 43                               | Day 71  | Day 99  | Day 141 | Day 183 | Day 225 | –                              |                                |  |
| Visit  | 1                               | 2                                  | 3      | Phone a | 4                                    | 5       | 6       | 7       | 8       | 9       | –                              | Unscheduled visit o | Early discontinuation visit p |
| Procedure/Assessment                                  |                                 |                                    |        |                    |                                      |         |         |         |         |         |                                |                                |  |
| Informed consent/assent d                         | X                               |                                    |        |                    |                                      |         |         |         |         |         |                                |                                |  |
| Inclusion/exclusion criteria                                 | X                               | X                                  |        |                    |                                      |         |         |         |         |         |                                |                                |  |
| Physical examinations  | X                               | X                                  | X      |                    | X                                    | X       | X       | X       | X       | X       | X                              | X                              | X  |
| Medical history  | X                               |                                    |        |                    |                                      |         |         |         |         |         |                                |                                |  |
| Concomitant medications                                      | X e                  | X                                  | X      |                    | X                                    | X       | X       | X       | X       | X       | X                              | X                              | X  |
| Adverse events f                                  | X                               | X                                  | X      | X                  | X                                    | X       | X       | X       | X       | X       | X                              | X                              | X  |
| Study drug compliance  |                                 |                                    | X      |                    | X                                    | X       | X       | X       | X       | X       |                                |                                | X  |
| Dispense subject diary                                       | X                               | X                                  | X      |                    | X                                    | X       | X       | X       | X       | X       |                                |                                | X  |
| Return and review subject diary                              |                                 | X                                  | X      |                    | X                                    | X       | X       | X       | X       | X       | X                              |                                | X  |
| Discontinuation/continuation/titration judgment g |                                 |                                    | X      | X                  | X                                    | X       | X       | X       | X       | X       |                                |                                |  |
| Vital signs and weight h                          | X                               | X                                  |        |                    | X                                    |         |         | X       |         | X       | X                              | X                              | X  |
| Clinical laboratory evaluations i                 | X                               | X                                  |        |                    | X                                    |         |         | X       |         | X       | X                              | X                              | X  |
| Study drug plasma concentration                              |                                 |                                    |        |                    | X                                    | X       |         | X       |         |         |                                |                                | X j                           |
| Urine drug screen  | X                               |                                    |        |                    |                                      |         |         |         |         |         |                                |                                |  |
| Urine pregnancy test k                            |                                 | X                                  | X      |                    | X                                    | X       | X       | X       | X       | X       | X                              | X                              | X  |
| Serum pregnancy test k                            | X                               |                                    |        |                    |                                      |         |         |         |         |         |                                |                                |  |
| 12-Lead ECG l                                     | X                               | X                                  |        |                    | X                                    |         |         | X       |         | X       | X                              | X                              | X  |
| EQ-5D-5L   | X                               |                                    |        |                    |                                      |         |         |         |         | X       |                                |                                | X  |
| Dispense study drug  |                                 | X                                  | X      |                    | X                                    | X       | X       | X       | X       | X       |                                |                                |  |
| Return unused medication                                     |                                 |                                    | X      |                    | X                                    | X       | X       | X       | X       | X       |                                |                                | X  |

AE = adverse event,  $\beta$ -hCG = beta-human chorionic gonadotropin, ECG = electrocardiogram, EQ-5D-5L = EuroQol 5 Dimensions 5 Levels.

a: Visit to be done within  $\pm 3$  days of the schedule. Each visit to be specified based on the date of Visit 2.

b: Visit to be done within  $\pm 7$  days of the schedule. Each visit to be specified based on the date of Visit 2.

c: To be completed by subjects who are withdrawn from the study after Visit 2 and before Visit 9 (for any reason). When a taper is provided after discontinuation, it should be performed 4 weeks after

- the last dose at the tapered dose and return unused medication.
- d: Informed consent/assent must be obtained prior to any study related procedure.
  - e: Prior and concomitant medication(s)
  - f: Adverse events will be collected from the time the subject signs the informed consent/assent form through the last visit. Serious adverse events will be collected for 28 days after the subject's last dose.
  - g: After Visit 4, if a subject experiences seizures, the investigator will end the 4 mg Maintenance Period and judge the transition to the 8 mg Titration Period based on the subject's tolerability and safety.
  - h: Height is to be measured only at Visit 1.
  - i: At Visit 1, confirm the results of the local laboratory analysis, if necessary. In case of the local laboratory analysis, the measurement of bicarbonate and magnesium are not mandatory at Visit 1, and after that should be conducted as scheduled
  - j: Collect blood samples if subjects are withdrawn from the study before Visit 7.
  - k: All female subjects will undergo the serum  $\beta$ -hCG pregnancy test at Visit 1. After Visit 2, only potentially pregnant female subjects will undergo the urine  $\beta$ -hCG pregnancy test.
  - l: At Visits 1 and 2, all subjects will undergo 3 consecutive ECGs at 5- to 10-minute intervals. After Visit 3, only subjects whose QTcF is measured as  $>450$  ms at any Visit will undergo additional 2 consecutive ECGs at 5- to 10-minute intervals (a total of 3 ECGs) to confirm the abnormality.
  - m: If Visit 1 and Visit 2 are the same day, only duplicate procedures/assessments will be performed once. If Visit 1 and Visit 2 are the same day and a result of serum pregnancy test can be assessed by the local laboratory during the day, urine pregnancy test at Visit 2 is not required.
  - n: For subjects who continue 4 mg QD, occurrence of AEs will be confirmed via telephone. Subjects who continue 2 mg QD or who are reduced from 4 mg QD to 2 mg QD during the 2 weeks of Weeks 3 and 4 will visit the investigational site via unscheduled visit within 4 weeks after starting study treatment and will be up-titrated to 4 mg QD.
  - o: At an unscheduled Visit, only the procedures/assessments that the investigators etc. has judged as necessary according to the subject's conditions will be performed.
  - p: If a taper is decided based on the judgment of the investigator, dispensing the study drug should be needed.

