#### 9.1.4 Follow-up Phase

Subjects who will finish or discontinue the study will conduct the follow-up visit 4 weeks after withdrawal of perampanel. When a taper is provided after discontinuation, it should be performed 4 weeks after the last dose at the tapered dose. Follow-up Visit is not required for subjects who will be switching to the commercial product and attend an End of Study Visit.

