##### 9.5.1.5.1 ADVERSE EVENTS

An adverse event (AE) is any untoward medical occurrence in a patient or clinical investigation subject administered an investigational product. An AE does not necessarily have a causal relationship with the medicinal product. For this study, the study drug(s) is(are) perampanel.

The criteria for identifying AEs in this study are:

- Any unfavorable and unintended sign (including an abnormal laboratory finding), symptom, or disease temporally associated with the use of an investigational product, whether or not considered related to the investigational product (Note: Every sign or

symptom should not be listed as a separate AE if the applicable disease [diagnosis] is being reported as an AE)

- Any new disease or exacerbation of an existing disease
- Any deterioration in nonprotocol-required measurements of a laboratory value or other clinical test (eg, ECG or x-ray) that results in symptoms, a change in treatment, or discontinuation of study drug
- Recurrence of an intermittent medical condition (eg, headache) not present pretreatment (Baseline)
- An abnormal laboratory test result should be considered an AE if the identified laboratory abnormality leads to any type of intervention, withdrawal of study drug, or withholding of study drug, whether prescribed in the protocol or not

All AEs, regardless of relationship to study drug or procedure, should be recorded beginning from the time the subject signs the study ICF through the last visit. SAEs will be collected for 28 days after the last dose.

Abnormal laboratory values should not be listed as separate AEs if they are considered to be part of the clinical syndrome that is being reported as an AE. It is the responsibility of the investigator to review all laboratory findings in all subjects and determine if they constitute an AE. Medical and scientific judgment should be exercised in deciding whether an isolated laboratory abnormality should be classified as an AE. Any laboratory abnormality considered to constitute an AE should be reported on the Adverse Event CRF.

Abnormal ECG (QTcF) results, if not otherwise considered part of a clinical symptom that is being reported as an AE, should be considered an AE if the QTcF interval is more than 450 ms and there is an increase of more than 60 ms from baseline. Any ECG abnormality that the investigator considers as an AE should be reported as such.

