| Study drug plasma concentration                              |                                    |        | X      | X                                    |         | X       |         |         |                                   | X g                      |                                | X g                           |
| Urine pregnancy test f                            | X                                  | X      | X      | X                                    | X       | X       | X       | X       | X                                 | X                                   | X                              | X  |
| 12-Lead ECG h                                     | X                                  |        | X      |                                      |         | X       |         | X       | X                                 | X                                   | X                              | X  |
| EQ-5D-5L   | X                                  |        |        |                                      |         |         |         | X       |                                   | X                                   |                                | X  |
| Dispense study drug  | X                                  | X      | X      | X                                    | X       | X       | X       | X       |                                   | X                                   |                                |  |
| Return unused medication                                     | X                                  | X      | X      | X                                    | X       | X       | X       | X       |                                   | X                                   |                                | X  |

β-hCG = beta-human chorionic gonadotropin, ECG = electrocardiogram, EQ-5D-5L = EuroQol 5 Dimensions 5 Levels.

- a: Visit to be done within ±3 days of the schedule. Each visit to be specified based on the date of Visit 2a.
- b: Visit to be done within ±7 days of the schedule. Each visit to be specified based on the date of Visit 2a.
- c: To be completed by subjects who are withdrawn from the study after Visit 2a and before Visit 9a (for any reason). When a taper is provided after discontinuation, it should be performed 4 weeks after the last dose at the tapered dose and return unused medication.

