##### 9.7.1.8.2 ADVERSE EVENTS

The AE verbatim descriptions (investigator terms from the CRF) will be classified into standardized medical terminology using the Medical Dictionary for Regulatory Activities (MedDRA). Adverse events will be coded to the MedDRA (Version 19.1 or higher) lower level term (LLT) closest to the verbatim term. The linked MedDRA preferred term (PT) and primary system organ class (SOC) are also captured in the database.

A treatment-emergent adverse event (TEAE) is defined as an AE that emerges during time from the first dose of study drug to the last visit or 28 days after the subject's last dose, whichever comes later, having been absent at pretreatment (Baseline) or

- Reemerges during treatment, having been present at pretreatment (Baseline) but stopped before treatment, or
- Worsens in severity during treatment relative to the pretreatment state, when the AE is continuous.

Only those AEs that are treatment-emergent will be included in summary tables. All AEs, treatment-emergent or otherwise, will be presented in subject data listings.

The TEAEs will be summarized. The incidence of TEAEs will be reported as the number (percentage) of subjects with TEAEs by SOC and PT. A subject will be counted only once within an SOC and PT, even if the subject experienced more than 1 TEAE within a specific SOC and PT. The number (percentage) of subjects with TEAEs will also be summarized by maximum severity (mild, moderate, or severe).

The number (percentage) of subjects with treatment-related TEAEs will be summarized by SOC and PT. Treatment-related TEAEs include those events considered by the investigator to be related to study treatment. The number (percentage) of subjects with treatment-related TEAEs will also be summarized by maximum severity (mild, moderate, or severe).

A subject data listing of all AEs leading to death will be provided.

The number (percentage) of subjects with treatment-emergent serious adverse events (SAEs) will be summarized by MedDRA SOC and PT. A subject data listing of all SAEs will be provided.

The number (percentage) of subjects with TEAEs leading to discontinuation from study drug will be summarized by MedDRA SOC and PT. A subject data listing of all AEs leading to discontinuation from study drug will be provided.

The TEAEs will be summarized for the Treatment Phase and the entire study period (ie, the Treatment Phase or the Extension Phase).

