5.4.3 Exploratory Efficacy Analyses

The number (percentage) of subjects with POS who achieved seizure-free during the entire study period and the corresponding 95% confidence interval (CI) will be calculated. The above analysis will also be summarized for the period between the Maintenance Period of the last evaluated dose and the date of data cutoff or the date of study discontinuation, whichever comes first.

The number (percentage) of subjects with POS who achieved seizure-free during the 26-week Maintenance Period of 4 mg and the 26-week Maintenance Period of the last

evaluated dose, and each corresponding 95% confidence interval (CI) will be calculated by types of partial seizure (ie, complex partial seizures, complex partial with secondarily generalized seizure, total of the 2 type).

The number (percentage) of subjects with POS who achieved seizure-free during the 52-week treatment of 4 mg (ie, 26-week Maintenance Period of 4 mg and 26-week Extension Phase) and the corresponding 95% CI will be calculated in subjects who had been scheduled to complete 52-week treatment and mITT analysis set. The above analysis will be performed by country, and will also be performed for subjects who completed 26-week maintenance period of 4 mg and did not enter extension phase excluded.

The number (percentage) of subjects with POS who achieved seizure-free during the 52-week treatment (ie, 26-week Maintenance Period and 26-week Extension Phase) and the corresponding 95% CI will be calculated in subjects who had been scheduled to complete 52-Week treatment and mITT analysis set. The 26-week Maintenance Period mentioned here is the Maintenance Period of the last evaluated dose. The above analysis will be performed by country, and will also be performed for subjects who completed 26-week maintenance period of 4 mg and did not enter extension phase excluded.

Median, Q1 and Q3 time to first seizure onset will be estimated by Kaplan-Meier method by country. The cumulative probability of the event (ie, seizure occurrence) at every 26 weeks will be calculated by country. Corresponding 2-sided 95% CIs will also be presented by country. The Follow-up Phase will not be included in this analysis. The above analysis will be summarized for the entire study period of 4 mg and the entire study period of the last evaluated dose, respectively.

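### Footnote c of Tables 3 and 4 contradicts Section 9.1.4 on whether completers who decline the Extension Phase have a Follow-up Visit, and collection of new non-serious AEs can stop up to 7 days before the TEAE window ends

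*Protocol*

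**What the plan says.** **Who has the visit.** Protocol Section 9.1.4 states: "Subjects who will finish or discontinue the study will conduct the follow-up visit 4 weeks after withdrawal of perampanel". The Synopsis and Section 9.1 say the same. The one exemption is: "Follow-up Visit is not required for subjects who will be switching to the commercial product and attend an End of Study Visit".

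The schedule tables are narrower. Table 3, footnote c: "To be completed by subjects who are withdrawn from the study after Visit 2 and before Visit 9 (for any reason". Table 4, footnote c: "To be completed by subjects who are withdrawn from the study after Visit 2a and before Visit 9a (for any reason". Table 5 has its own Follow-up column, but that table covers the Extension Phase only.

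**Who could fall between the two.** Under Section 9.1.3, a subject enters the Extension Phase only by agreeing to continue. SAP Section 5.2.2 tabulates subjects who do and do not enter it. SAP Section 5.4.3 plans an analysis with "subjects who completed 26-week maintenance period of 4 mg and did not enter extension phase excluded".

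**When the visit happens.** The Follow-up columns place it 4 weeks after the last dose. They carry footnote b in Tables 3 and 4; in Table 4 it reads "Visit to be done within ±7 days of the schedule. Each visit to be specified based on the date of Visit 2a", and Table 3 has the equivalent with Visit 2. In Table 5, footnote a gives the same ±7 days. Section 9.1.4 gives no window.

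**What is collected and counted.** Section 9.5.1.5.1 records AEs through the last visit and adds: "SAEs will be collected for 28 days after the last dose". Section 9.7.1.8.2 describes a TEAE as "defined as an AE that emerges during time from the first dose of study drug to the last visit or 28 days after" the last dose, taking the later of the two dates. SAP Section 8.3 repeats that definition.

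**The concern.** Sites run visits from the schedule tables. If the footnote is followed, a completer who leaves at Visit 9 or 9a has no off-drug visit, although the body text requires one. The Follow-up column of Tables 3 and 4 holds a physical examination, concomitant medications, AEs, diary return, vital signs and weight, laboratory tests, a urine pregnancy test and an ECG.

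Some of this feeds planned outputs. SAP Section 8.1 excludes Follow-up Phase data from summary tables except for AEs, duration of exposure and TEMAVs, and SAP Section 5.6.3 summarises TEMAVs with the Follow-up Phase included. Safety is a secondary objective, and Section 7.2 plans a safety comparison with Study 335. If sites read the rule differently, the period just after stopping the drug would be observed for some leavers and not for others.

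The second issue concerns subjects who do have the visit. The TEAE definition can reach past the date on which non-serious events stop being recorded, so the AE tables would describe a window that was only partly collected.

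**Working it through.** **Reproducing the schedule.** Visit 9 is at Week 32: 1 + 32 × 7 = Day 225. Visit 9a is at Week 30: 1 + 30 × 7 = Day 211. Both match Tables 3 and 4. The Follow-up Visit is nominally 4 × 7 = 28 days after the last dose.

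**Who is covered, by route out of the study.**

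| Route | Synopsis, 9.1, 9.1.4 | Schedule tables |
|---|---|---|
| Withdrawn before Visit 9 or 9a | Visit required | Visit required (Tables 3, 4) |
| Completes Visit 9 or 9a, does not enter the Extension Phase | Visit required | Outside footnote c; not in Table 5 |
| Leaves during the Extension Phase, no switch to marketed drug | Visit required | Visit required (Table 5) |
| Switches to marketed drug with an End of Study Visit | Exempt | Exempt (Table 5, footnote i) |

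The sources disagree only in the second row.

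**What depends on the visit in that row.** These duties run to Day 28 whether or not a visit takes place:
- SAE collection (Sections 9.5.1.5.1 and 9.5.4.1; also Table 3 footnote f and Table 4 footnote d);
- follow-up of AEs already recorded, to Day 28 or resolution if sooner (Section 9.5.1.5.1);
- reporting of pregnancies conceived within 28 days of the last treatment (Section 9.5.4.2).

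New non-serious AEs, laboratory tests, ECG, pregnancy test and diary return do depend on it.

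**Timing, with the last dose as Day 0.** The permitted range is 28 − 7 = Day 21 to 28 + 7 = Day 35. The TEAE window ends at max(last visit, 28). Collection of new non-serious AEs ends at the last visit.

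| Follow-up Visit | TEAE window ends | Days not collected for new non-serious AEs |
|---|---|---|
| Day 21 | Day 28 | 28 − 21 = 7 (7/28 = 25%) |
| Day 28 | Day 28 | 0 |
| Day 35 | Day 35 | 0 |

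**The anchor in footnote b.** It sets each visit from Visit 2 (or 2a), but the column heading counts from the last dose. These do not fit together. In Table 3, a last dose on Day 99 puts the nominal Follow-up Visit at 99 + 28 = Day 127, and a last dose on Day 183 puts it at 183 + 28 = Day 211. No fixed day counted from Visit 2 serves both. Table 5 footnote a has the same feature, with the start of the Extension Phase as its anchor.

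**The case against.** The strongest reply is that the protocol already requires the visit. Three places in the text say so, and Section 11.2 binds investigators to the protocol as a whole rather than to one footnote. That stands. A reader might infer from the tables that completers who decline the Extension Phase get no follow-up; the documents do not support this. They contain a contradiction, and what happens in practice depends on which passage a site follows.

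A reader might also infer that such a subject's whole 28-day safety window goes unobserved. That is not supported either, because SAE collection, pregnancy reporting and follow-up of known AEs do not hang on the visit.

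It is fair to add that the analysis impact is limited. Follow-up seizure data go only to listings (SAP Section 8.2), the time-to-event analyses leave out the Follow-up Phase (SAP Section 5.4.2), and TEAEs are counted as subjects rather than per person-time, so unobserved days inflate no denominator. All of that stands. It leaves a possible undercount of subjects with a late non-serious TEAE or an off-drug TEMAV.

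On timing, Day 21 is the edge of a symmetric window around Day 28, and many visits will fall on or after Day 28. That limits the size of the gap but does not close it.

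The taper wording might look like a further conflict. It is not one: Sections 9.4.1 and 9.1.4 both speak of a taper only in connection with discontinuation.

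**Conclusion.** The point holds as an inconsistency that should be repaired. Footnote c of Tables 3 and 4 and the body text give different answers for one defined group: subjects who complete Visit 9 or 9a and do not enter the Extension Phase. The SAP expects that group, but the documents give no count or rate for it, so the number affected cannot be computed. If a site follows the tables, the loss per such subject is the off-drug visit procedures and new non-serious AEs after the last visit.

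For subjects who have the visit, the gap is at most 7 of 28 days, for new non-serious AEs only, and it is zero when the visit falls on Day 28 or later. This assumes that the ±7 days apply around 4 weeks after the last dose, as the column headings and footnotes imply. The mismatched anchor in footnote b is a separate, smaller drafting fault.

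The primary and other efficacy analyses are not affected.

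**What to change.** 1. Reconcile footnote c of Tables 3 and 4 with Section 9.1.4, Section 9.1 and the Synopsis, so that all of them name the same subjects and say explicitly what applies to a completer who does not enter the Extension Phase.
2. Correct the date anchor for the Follow-up Visit in footnote b of Tables 3 and 4 so that it agrees with the column heading, and check footnote a of Table 5 for the same reason.
3. Align the collection period for non-serious AEs with the TEAE window. One way is to state that new non-serious AEs are collected to the later of the last visit and Day 28 after the last dose. A telephone contact would be enough when the visit falls earlier; Section 9.5.5 already uses telephone for subjects who stop attending.

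The cost is footnote and section wording in an amendment, plus a small amount of extra data collection. No analysis method changes.
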